5.5.2 Dispensing the study drug

Each study site will be supplied with study drug in packaging of identical appearance. Due to the open-label design of the study the study drug is not specifically labelled with medication numbers.

5.5.3 Handling of study and additional treatment

5.5.3.1 Handling of study treatment

Study treatment must be received by a designated person at the study site, handled and stored safely and properly, and kept in a secured location to which only the investigator and designees have access. Upon receipt, all study treatment must be stored according to the instructions specified on the labels. Clinical supplies are to be dispensed only in accordance with the protocol. Technical complaints are to be reported to the respective Novartis Germany Quality Assurance.

5.5.3.2 Handling of additional treatment

Dermatologic study site personnel will instruct patients how to contact their lifestyle intervention trainer in order to participate in the lifestyle intervention program. For patients randomized to receive concomitant lifestyle intervention **it is mandatory to participate in the lifestyle intervention and to show up to the counseling appointments scheduled**. All patient materials which are part of the lifestyle intervention (Lese-/Arbeitsbuch, information flyer, activity tracker, Theraband, scale, tape measure) are given to patients in arm B at randomization visit (study visit 2).

5.5.4 Instructions for prescribing and taking study treatment/ for participating in the lifestyle intervention program

The first study treatment administration will occur at baseline (visit 2) after the inclusion/exclusion criteria have been confirmed and all study scheduled assessments have been performed.

All doses of study treatment are administered at the study site by study site personnel or by the patient himself under the supervision of study site personnel. All study assessments, including blood withdrawal and completion of Patient Reported Outcomes (PROs), i.e. DLQI, should be completed prior to the injection of study treatment. The flow of work and the consecutive steps of assessments including Clinical Outcome Assessments (COA) are given in Section 6.

In single, **exceptional** cases where a visit needs to be skipped e.g. due to business/ working travels of the patient, home administration of study treatment by the patient himself without supervision is allowed at the discretion of the investigator for up to one time per patient between week 8 and week 24. In these cases the investigator is allowed to provide the patient at most one dose of study treatment (2 pre-filled syringes) in advance. Study treatment must be transported in a suitable cooled bag, which will be provided at the study sites. During home administrations subjects are expected to contact the investigator/site staff in case they are experiencing any AE/SAE or have any concerns or are unable for any reason to take the study treatment as prescribed. A visit should be scheduled as close as possible to the time of the per protocol planned visit which had to be skipped. At this visit all assessments of the skipped visit should be performed but no study drug will be administered.

Irrespective of self-administration or administration by study site personnel, the **first** Secukinumab administration at baseline (visit 2) will take place at the study site. In case the patient considers self-administration he must be instructed through the site staff by explaining

the Instructions For Use (IFU) on how to self-inject via the pre-filled syringe. After providing detailed explanations/instructions, subjects will then be asked to raise any questions. Thereafter, they will proceed with self-injection. In case of self-administration the investigator is obliged to make sure that injections are performed correctly and exactly as prescribed. In case of doubt about patient's ability or willingness to perform injections reliably and correctly the investigator can decide to prohibit self-administration.

The study treatment solution must be injected in **non-affected** areas of the skin.

Pre-filled syringes should be kept at 2 to 8° C (36° F and 46° F), never be frozen, and should be protected from light. Prior to administration, the boxes containing the pre-filled syringes should be allowed to adapt to room temperature unopened for about 20 minutes before administration. Patients should return used syringes to the study site for drug accounting and disposal.

All dosages prescribed and dispensed to the patient and all dose changes during the study must be recorded on the Dosage Administration Record CRF

The investigator must promote compliance by instructing the patient to take the study treatment exactly as prescribed and by stating that compliance is necessary for the patient's safety and the validity of the study.

The lifestyle intervention program has scheduled counseling visits where the patients meet their trainer. These visits are defined in a separate manual. For patients randomized to concomitant lifestyle intervention it is mandatory to participate in the program and to show up for the counseling visits. Participation in the lifestyle intervention counseling visits must be recorded in the eCRF. The investigator should explain to the patient that participation in the program and showing up to all counseling visits is mandatory, necessary for the validity of the study and yields benefit for the patient.

5.5.5 Permitted dose adjustments and interruptions of study treatment/ interruptions of lifestyle intervention

Treatment interruptions and dose adjustments of study treatment are **not** permitted. If a dose was not or incorrectly administered, this deviation must be recorded on the Dosage Administration Record CRF.

The same applies for the lifestyle intervention: Stopping participation (e.g. not showing up to counseling visits) or skipping counseling visits of the program is not permitted. Participation in the lifestyle intervention program must be recorded in the eCRF.

5.5.6 Rescue medication

Use of rescue medication is not permitted in this study.

5.5.7 Concomitant medication

The investigator must instruct the patient to notify the study site about any new medications he/she takes after the patient was enrolled into the study. All medications, procedures and significant non-drug therapies (including physical therapy and blood transfusions) administered

after the patient was enrolled into the study must be recorded in the concomitant medications / significant non-drug therapies eCRF.

Each concomitant drug must be individually assessed against all exclusion criteria/prohibited medication. If in doubt the investigator should contact the Novartis medical monitor before randomizing a patient or allowing a new medication to be started.

Please see table 5-1 for details on prohibited and concomitant medication.

5.5.8 Prohibited medication

Use of the treatments displayed in the below table is NOT allowed during the respective period.

Table 5-1 Prohibited treatments by period (for any indication)

| Prohibited treatments during the core study^{a, b, g, h} | Washout period (before baseline, i.e. visit 2) |
|---|--|
| Secukinumab and other IL-17 and IL-17 receptor antagonists (e.g. Ixekizumab, Brodalumab) | No prior use allowed |
| Biologicals targeting TNF (e.g. Etanercept, Adalimumab, Infliximab) | No use 1 year prior to baseline visit (visit 2) allowed |
| Alefacept, Briakinumab, Efalizumab, Ustekinumab | 6 month |
| Biological immunomodulating agents other than above | 12 weeks |
| Other systemic immunomodulating treatments (e.g. Methotrexate, cyclosporine A, corticosteroids ^c , cyclophosphamide) | 4 weeks |
| Other systemic psoriasis treatments ^d (e.g. retinoids, fumarates, apremilast) | 4 weeks |
| Photochemotherapy (e.g. systemic PUVA, Balneo-PUVA, topical PUVA) | 4 weeks |
| Phototherapy (e.g., UVA, UVB, Balneo-Phototherapy without psoralen derivatives) | 2 weeks |
| Topical treatment that is likely to impact signs and symptoms of psoriasis (vitamin D analogues, Tacrolimus, Pimecrolimus potent corticosteroids, salicylvaseline, salicylic acid, lactic acid, tar, alpha-hydroxy or fruit acids) ^e . | 2 weeks |
| Live virus vaccinations ^{***} | 6 weeks |
| Any investigational treatment (including anti IL23p19) or participation in any interventional trial | 4 weeks or 5 half-lives (whichever is longer) |
| The following glucose-lowering agents: Insulin, sulfonylurea agents/analogues, thiazolidinediones/glitazones | 12 weeks |

It is forbidden to start therapy with one of the following medications during the core study^f:

Prohibited treatments during the core study^{a, b, g, h}

Washout period
(before baseline, i.e. visit 2)

Cholesterol- or lipid lowering agents (e.g. HMG-CoA-inhibitors/statins, fibrates, nicotinic acid, ezetimibe, colestyramin, colestipol)

Antihypertensive drugs (e.g. ACE-inhibitors, angiotensin-receptor antagonists, β -blockers, aldosterone receptor antagonists, diuretics, nitrates, calcium channel blockers (e.g. Verapamil, Nifedipin), Aliskiren, Clonidin, α 1 receptor antagonists (e.g. Doxazosin), Dihydralazin, Minoxidil, Clonidin, Moxonidin or Methyldopa)

Glucose-lowering agents (e.g. Metformin, DPP4 inhibitors, SGLT2 inhibitors, GLP1 analogues etc.)

*If a patient has already been taking one of these medications on a stable dose for at least 12 weeks before baseline (visit 2), he can be enrolled in the study and continue to take them during the study, except for the glucose-lowering agents insulin, sulfonylurea agents/analogues and thiazolidinediones/glitazones, which are **not** allowed during the core study.*

Dose adjustments or withdrawal of the following medications should be avoided during the core study:

Cholesterol- or lipid lowering agents (e.g. HMG-CoA-inhibitors/statins, fibrates, nicotinic acid, ezetimibe, colestyramin, colestipol)

Prohibited treatments during extension period

There are **no treatment restrictions** during the extension period, any treatments can be used.

^a If a prohibited treatment of psoriasis was used during the study, the subject should discontinue use of the prohibited treatment if he/she wishes to continue in the study.

^b In case of undue safety risk for the subject, the subject should discontinue study treatment at the discretion of the investigator. If the subject received a live virus vaccination during the study, the subject must discontinue study treatment.

^c Oral, i.v., i.m., s.c.,. Exceptions: Inhalative corticosteroids (CS) with only a topical effect (e.g., to treat asthma) are not considered "systemic immunomodulating treatments" and are therefore acceptable as co-medication. The use of intra-articular and peri-articular corticosteroids is permitted throughout the study for treatment of symptoms of psoriatic arthritis that cannot be sufficiently controlled by study treatment and/or concomitant non-steroidal anti-inflammatory drugs (NSAIDS).

^d There is no restriction on the use of anti-histamines and on the use of corticosteroids in the eye, nose or the ear

^e **Mild to moderate topical corticosteroids are allowed only during the screening period if used only on the face, scalp and/or anogenital area. The use must be stopped 12 hours prior to first study medication administration. Urea (up to 5%) is allowed throughout the complete study, but must also be stopped 12 hours prior to each study visit.**

^f **Urgent medical cases are excluded from this regulation.** These cases have to be documented in the eCRF.

*** Inactivated virus vaccinations are allowed

^g If study treatment for psoriasis (i.e. secukinumab) is discontinued during the core study, then all restrictions for prohibited psoriasis treatments are lifted and the patient may be treated with concomitant topical, conventional systemic and/or biologic psoriasis treatments and/or phototherapy.

^h If the lifestyle intervention is discontinued during the core study, then all restrictions for prohibited treatments for metabolic syndrome are lifted and the patient may be start other concomitant treatments for metabolic syndrome and/or change the dosage of treatments for metabolic syndrome that are already being administered.

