5.6.2 Discontinuation of study treatment

Discontinuation of study treatment for a patient occurs when study treatment (Secukinumab or lifestyle intervention or both) is stopped earlier than the protocol planned duration and can be initiated by either the patient or the investigator.

The investigator must discontinue study treatment (Secukinumab or lifestyle intervention or both) for a given patient if, on balance, he/she believes that continuation would negatively impact the risk/benefit of trial participation.

Study treatment must be discontinued under the following circumstances:

- Patient wish
- Pregnancy (see Section 6.5.6 and Section 7.6)
- Use of prohibited treatment as per recommendations in Table 5-1
- Any situation in which study participation might result in a safety risk to the patient
- Emergence of the following adverse events: AEs that in the judgment of the investigator/qualified site staff, taking into account the subject's overall status prevent the subject from continuing study treatment

- Any laboratory abnormalities that in the judgment of the investigator, taking into consideration the subject's overall status, prevents the subject from continuing participation in the study
- Severe infections

If discontinuation of study treatment occurs during the core study, the patient should NOT be considered withdrawn from the study.

After study treatment discontinuation (i.e. discontinuation of secukinumab, lifestyle intervention or both) the patient will continue to attend regular study visits as per visit schedule and all assessments will be performed as planned. If one study treatment is discontinued (i.e. secukinumab or lifestyle intervention) this should not lead to discontinuation of the other, unless there is a reason for discontinuation of the other (see above for a list of reasons for discontinuation).

If a study treatment is discontinued, adequate replacement for this treatment may be sought outside of the study despite continued study participation:

- If secukinumab is discontinued, adequate concomitant drug treatment for psoriasis may be administered outside of the study. This does not require withdrawal of the patient from the study. In this case, there are no restrictions for concomitant psoriasis treatments (including topical, conventional systemic and biological drug treatments and phototherapy), even if the patient is still participating in the core or extension study period.

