5.6.5 Early study termination by the sponsor

The study can be terminated by Novartis at any time for any reason. This may include reasons related to the benefit risk assessment of participating in the study, practical reasons, or for regulatory or medical reasons (including slow enrolment). Should this be necessary, the patient must be seen as soon as possible and treated as a prematurely withdrawn patient. The investigator may be informed of additional procedures to be followed in order to ensure that adequate consideration is given to the protection of the patient's interests. The investigator will be responsible for informing the Institutional Review Board/Independent Ethics Committee (IRBs/IECs) of the early termination of the trial.

6 Visit schedule and assessments

Table 6-1 lists all of the assessments and indicates with an "x" when the visits are performed.

Patients should be seen for all study visits on the designated day, or as close to it as possible. Recommended study visit windows are +/- 2 days for visits 2 – 6, +/- 5 days for visits 7 – 12 and +/- 7 days for visits E1 – E3. The same visit windows are recommended for the lifestyle intervention visits associated to the study visits.

Missed or rescheduled visits should not lead to automatic discontinuation. Patients who prematurely discontinue the study for any reason should be scheduled for a visit as soon as possible, at which time all of the assessments listed for the final visit will be performed. In case of premature discontinuation during the core study the final visit is the week 28 visit, in the case of premature discontinuation during the extension period the final visit is the week 56 visit. At this final visit, all dispensed investigational product should be reconciled and the adverse event and concomitant medications reconciled on the CRF.

Table 6-1 lists assessments that are recorded in the clinical database (marked “X” if entered via the eCRF or “C” if entered centrally, e.g. via a central laboratory) and assessments that are source documentation only (marked “S”). Assessments that are source documentation only will not be entered into the eCRF.

If for any reason the subject is a screen failure, the subject may be re-screened. There is no restriction on the number of times a potential subject may be re-screened or on how much time must pass from the date of screen failure and the date of re-screening.

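### Table 5-1 footnote a makes stopping a prohibited psoriasis treatment a condition of staying in the study, whereas Section 5.6.2 stops at most the study treatment and keeps the patient in follow-up

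*Protocol*

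**What the plan says.** Table 5-1 in Protocol 5.5.8 lists the treatments prohibited during the core study, and several footnotes hang on its heading. Footnote a covers a patient who has used a prohibited psoriasis treatment: "the subject should discontinue use of the prohibited treatment if he/she wishes to continue in the study". Footnote g covers the time after secukinumab has been discontinued: "then all restrictions for prohibited psoriasis treatments are lifted".

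Protocol 5.6.2 lists the reasons for which study treatment must be stopped. One is "Use of prohibited treatment as per recommendations in Table 5-1", which sends the site back to the table and its footnotes. The same section then fixes the patient's status: "If discontinuation of study treatment occurs during the core study, the patient should NOT be considered withdrawn from the study". It adds that "the patient will continue to attend regular study visits as per visit schedule and all assessments will be performed as planned". It also allows any other psoriasis therapy once secukinumab has been stopped, without withdrawal.

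For patients who leave the study itself, Protocol Section 6 (visit schedule) applies: "Patients who prematurely discontinue the study for any reason should be scheduled for a visit as soon as possible", with the final-visit assessments done then. Protocol 9.4.3 and SAP 2.5.3 score a patient without a valid Week 28 PASI as a non-responder. SAP 5.5 assigns visits by study day, and its Week 28 window is Day 184-211.

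**The concern.** The two rules attach different consequences to the same event. Take a patient on secukinumab who starts a prohibited psoriasis treatment and wants to keep it. Under 5.6.2 secukinumab is stopped and the patient is followed to Week 28. Under the plain words of footnote a, keeping the treatment is incompatible with continuing in the study. Because the 5.6.2 trigger refers to Table 5-1, a site checking what to do can arrive at footnote a.

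The primary endpoint is at stake. A patient kept under 5.6.2 supplies an observed Week 28 PASI, which may be a response. A patient who leaves early usually supplies none and is counted as a non-responder. The difference would come from a footnote, not from the treatment. The only planned sensitivity analysis, the center-stratified CMH test in SAP 2.5.4, uses the same responses and would not reveal it.

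**Working it through.** **1. The rules side by side**

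| Place | Trigger | Consequence |
|---|---|---|
| Table 5-1, footnote a | Prohibited psoriasis treatment used | Should stop it in order to continue in the study |
| Table 5-1, footnote b | Live virus vaccination received | Must stop study treatment |
| Protocol 5.6.2 | Prohibited treatment used, per Table 5-1 | Study treatment stopped; not withdrawn; all assessments continue |
| Table 5-1, footnote g | Secukinumab already stopped | Psoriasis-treatment restrictions no longer apply |

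Footnote b names study treatment, as 5.6.2 does. Footnote a names the study. Footnote g starts from a later state than footnote a: once secukinumab has stopped, no psoriasis treatment is prohibited, so nothing is left for footnote a to act on. The conflict is therefore between footnote a and 5.6.2 only.

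**2. Whether an early exit loses the Week 28 value**

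Inputs: visit days from Protocol Table 6-1, recommended visit windows from Protocol Section 6, analysis window from SAP 5.5.

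- Post-baseline core visits: Days 8, 15, 22, 29, 57, 85, 113, 141, 169 and 197. Nine of the ten are before Day 184.
- The latest of those nine, with its recommended window: 169 + 5 = Day 174.
- Gap to the opening of the Week 28 window: 184 - 174 = 10 days.

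A final visit held at or soon after any of these nine visits is thus mapped to Week 24 or earlier, and the patient is imputed as a non-responder. The loss is not automatic. If use is found at Day 169 and the final visit takes place 15 to 42 days later (184 - 169 = 15; 211 - 169 = 42), the PASI is a Week 28 value. The same holds for any later exit with a final visit on Day 184-211.

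Section 6 also says: "In case of premature discontinuation during the core study the final visit is the week 28 visit". Read with its context, this tells the site which assessments to perform. It does not change the study day, and study day is what the SAP uses for mapping.

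**3. Scale**

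The sample size is not in question. For 81% vs 90%, two-sided 0.05 and 90% power, the two-proportion formula gives 320 per arm. With continuity correction, (320/4) × [1 + √(1 + 4/(320 × 0.09))]² = 341.9, so 342, as stated. The planned 380 equals 342/0.90; the 10% allowance is inferred, not stated.

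Each would-be responder lost by early exit lowers that arm's rate by 1/380 = 0.26 points.

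The documents give no exit rate, so the following range is assumed and shows scale only. If a share w of each arm left early and all were imputed, the expected difference would be 9 × (1 - w) points:

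| w | Difference | Power at 380 per arm (continuity-corrected) |
|---|---|---|
| 0 | 9.00 | 93.0% |
| 1% | 8.91 | 91.3% |
| 2% | 8.82 | 89.4% |
| 5% | 8.55 | 83.4% |

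This supposes that those who leave would have responded at their arm's planned rate, and that a site reading 5.6.2 would have kept every one of them. It is not evidence that such exits occur.

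**The case against.** The strongest reply is that the protocol already settles the matter. Section 5.6.2 says, with the negative in capitals, that the patient is not withdrawn, and that other psoriasis therapy after secukinumab does not require withdrawal. Footnote a says should and orders no withdrawal. The exits set out in 5.6.3 to 5.6.5 are withdrawal of consent, loss to follow-up and termination by the sponsor; prohibited medication is not among them. A site that reads both places would keep the patient. All of this stands. It makes the harmful reading unlikely, but it does not make the footnote correct.

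A reader might go further than the documents allow in four ways.

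- **Footnotes a and g contradict each other.** They do not; g is a carve-out that begins when secukinumab ends.
- **Every exit at a core visit before Week 28 is lost.** Section 6 asks for a final visit as soon as possible, not on the same day, and the visit windows are recommendations. A visit on Day 184-211 counts.
- **The plan does not say how to score a Week 28 PASI obtained on other therapy.** The intent-to-treat FAS (SAP 2.2), the retention of prohibited-medication users in every analysis (SAP 5.4, COMD01 and COMD02) and the visit rules (SAP 5.5 and 5.5.1) together imply that it is used as observed.
- **The problem can be sized by rescoring patients on other therapy at Week 28.** Those patients were retained, so this measures a different question from loss through early exit.

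**Conclusion.** The point holds as a wording error in an operative rule. Footnote a conflicts with 5.6.2, and 5.6.2 states the intended handling. The consequence, an obtainable Week 28 PASI turned into an imputed non-response, needs three things together: a patient who will not stop the prohibited treatment, a site that takes footnote a as ending participation in spite of 5.6.2, and a final visit before Day 184. The documents give no frequency for any of these and no reason to expect them to differ by arm. The effect on the primary result is probably small, and its size cannot be derived from the documents. No fault in the sample size, the analysis sets or the scoring of observed values follows from this point.

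**What to change.** In Table 5-1, footnote a, replace the words *continue in the study* with: *continue secukinumab study treatment; otherwise secukinumab is stopped and the subject stays in the study and attends Week 28 per 5.6.2 and footnote g*. Leave the 5.6.2 bullet as it is. The cost is one phrase in the protocol; the sample size, the data collection and the primary analysis do not change.

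Separate and optional: SAP 2.5.4 could add a supportive rerun of the primary logistic model that counts as non-responders the patients on other psoriasis therapy at the Week 28 assessment. The data exist, since Protocol 5.5.7 requires that medications and procedures "must be recorded in the concomitant medications / significant non-drug therapies eCRF". This rerun addresses a different estimand and does not remedy early exits, because those patients are non-responders in both analyses. It should not be presented as the answer to the footnote problem.
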